1. INTRODUCTION

The purpose of this statistical analysis plan (SAP) is to provide details of the statistical analyses for Study Protocol 1002-043 *A Randomized, Double-Blind, Placebo-Controlled Study to Assess the Effects of Bempedoic Acid (ETC-1002) on the Occurrence of Major Cardiovascular Events in Patients with, or at High Risk for, Cardiovascular Disease Who are Statin Intolerant*, Amendment 5 (24 September 2020).

2. STUDY OBJECTIVES

2.1. Primary Objective

The primary objective is to evaluate whether administration of bempedoic acid 180 mg/day versus placebo reduces the risk of major adverse cardiac event (MACE) in patients with, or at high risk for, cardiovascular disease (CVD) who are statin intolerant. This will be assessed with a composite primary efficacy endpoint that includes time to first occurrence of cardiovascular (CV) death, nonfatal myocardial infarction (MI), nonfatal stroke, or coronary revascularization.

2.2. Secondary Objectives

The secondary objectives include:

- To evaluate whether long-term treatment with bempedoic acid 180 mg/day versus placebo reduces the risk of other clinical endpoints of CV morbidity and mortality and all-cause mortality
- To evaluate the effect of long-term treatment with bempedoic acid 180 mg/day versus placebo on low-density lipoprotein cholesterol (LDL-C) and high-sensitivity C-reactive protein (hs-CRP)
- To evaluate the long-term safety and tolerability of bempedoic acid 180 mg/day compared to placebo
- To evaluate the 12-month impact of treatment with bempedoic acid 180 mg/day versus placebo on absolute change in hemoglobin A_{1C} (HbA_{1C}) in patients with inadequately controlled type 2 diabetes mellitus (HbA_{1C} of 7% or greater at baseline)
- To evaluate whether long-term treatment with bempedoic acid 180 mg/day versus placebo reduces the risk of new-onset type 2 diabetes

2.3. Tertiary Objective

- To evaluate the effect of long-term treatment with bempedoic acid 180 mg/day versus placebo on non-high-density lipoprotein cholesterol (non-HDL-C), total cholesterol (TC), high-density lipoprotein cholesterol (HDL-C), triglycerides (TG), HbA_{1C}, and fasting glucose

3. STUDY ENDPOINTS

3.1. Primary Efficacy Endpoint

- Time to first occurrence of a MACE, where MACE is defined as the composite endpoint of CV death, nonfatal MI, nonfatal stroke, or coronary revascularization (MACE-4)

3.2. Secondary Efficacy Endpoints

3.2.1. Key Secondary Efficacy Endpoints

Key secondary efficacy time-to-event endpoints include, in hierarchical order:

1. Time to first occurrence of the composite endpoint of CV death, nonfatal MI, or nonfatal stroke (MACE-3)
2. Time to first occurrence of (fatal + nonfatal) MI
3. Time to first occurrence of coronary revascularization
4. Time to first occurrence of (fatal + nonfatal) stroke
5. Time to CV death
6. Time to all-cause mortality

3.2.2. Additional Secondary Time-to-Event Endpoints

Additional secondary efficacy time-to-event include:

- Time to first occurrence of the composite endpoint of all-cause mortality, nonfatal MI, nonfatal stroke, or coronary revascularization
- Time to first occurrence of 5-component composite endpoint of CV death, nonfatal MI, nonfatal stroke, coronary revascularization, or hospitalization for unstable angina (MACE-5)
- Time to first occurrence of nonfatal MI
- Time to fatal MI
- Time to first occurrence of nonfatal stroke
- Time to fatal stroke
- Time to first occurrence of (fatal + nonfatal) hemorrhagic stroke
- Time to first occurrence of (fatal + nonfatal) nonhemorrhagic stroke
- Time to hospitalization for unstable angina
- Time to first occurrence of new-onset type 2 diabetes mellitus (NODM)

3.2.3. Secondary Efficacy Lipid and Biomarker Endpoints

- Percent change from baseline to Month 6 in LDL-C
- Percent change from baseline to Month 6 in hs-CRP
- Change from baseline to Month 12 in HbA_{1C} in patients with inadequately controlled type 2 diabetes mellitus

3.3. Tertiary Lipid and Biomarker Endpoints

- Absolute change and percent change from baseline to Months 3, 6, 12, 24, then every 6 months through the end of study in LDL-C
- Absolute change and percent change from baseline to Months 3, 6, 12, 24, then every 6 months through the end of study in non-HDL-C, TC, HDL-C, and TG
- Percent change from baseline to Month 12 and at the end-of-study (EOS) in hs-CRP
- Change from baseline to Month 3, 6, 12, then every 6 months through the end of study in HbA_{1C}
- Change from baseline to Month 3, 6, 12, then every 6 months through the end of study in fasting glucose

3.4. Safety Endpoints

- Adverse events (AEs) and adverse events of special interest (AESIs)
- Vital signs
- Clinical laboratory measures

4. STUDY DESIGN

4.1. General Description

[figure not shown]
This is a Phase 3, multicenter, randomized, double-blind, placebo-controlled, parallel-group study assessing the occurrence of MACE in patients with, or at high risk for, CVD who are unable to tolerate statin therapy. The study is conducted at approximately 1200 clinical sites in 32 countries.

Following signing of an informed consent document prior to any study procedures, screening (Visit S1) occurred approximately 5 weeks prior to Day 1 (Visit T1) but can be extended for an additional 5 weeks if needed to adjust background medical therapy or for other reasons. All eligible patients will return at Week -4 (Visit S2, 4 weeks prior to Day 1) to initiate a 4-week Run-in Period with single-blind (blinded to patient only) placebo once daily that will include assessment of tolerability and investigational medicinal product (IMP) adherence. On Day 1 (Visit T1), approximately 14,000 eligible patients will be randomized 1:1 to receive either double-blind bempedoic acid 180 mg (n ~ 7,000) or placebo (n ~ 7,000) once daily. Randomized patients will return for clinic visits at Month 1 (Visit T2), Month 3 (Visit T3), and Month 6 (Visit

T4). Following Month 6, patients will be contacted every 3 months (alternating with a phone visit and a clinic visit) for the remainder of the study.

Patients who discontinue IMP for any reason are strongly encouraged to remain in the study to be evaluated for efficacy and safety endpoints and will be expected to continue study visits or agree to some other form of contact through the study closeout.

Figure 1: 1002-043 Study Design

4.2. Maintenance of Blinding

During the Treatment Period, Sponsor, site personnel, CRO, and patient are all unaware of patient's treatment assignment. Blinding of treatment must be maintained for all patients unless, in the opinion of the investigator, the safety of the patient may be at risk. If the blind must be broken prior to consultation with the Medical Monitor, contact must be made within 24 hours of breaking the blind.

Unblinding of IMP will NOT automatically discontinue the patient from the study. Any patient for whom the blind is broken will be permanently discontinued from IMP but should continue in the study.

Post-randomization values for individual laboratory measures for LDL-C, non-HDL-C, TC, TG, and hs-CRP are not available to blinded personnel from the clinical site, the patient, the Sponsor, or the CRO during the study.

4.3. Study Closeout

The study will continue until all the following criteria have been met:

1. at least 1,620 patients have experienced an adjudicated primary 4-component MACE (CV death, nonfatal MI, nonfatal stroke, or coronary revascularization),
2. at least 810 patients have experienced an adjudicated 3-component MACE (CV death, nonfatal MI, or nonfatal stroke) and
3. 24 months have elapsed since the last patient was randomized.

During the study closeout period (when the patients' End of Study (EOS) Visits will be scheduled), each patient still in the study will be required to complete an in-clinic visit which is

designated as the EOS Visit and perform the procedures according to Protocol Appendix 1, Schedule of Events. Patients who are still on IMP at the visit will be asked to end study treatment.

A post-treatment telephone visit will occur 30 days (\pm 10 days) after the EOS visit to assess AEs, SAEs and identify potential clinical endpoints.

[figure not shown]
During the study closeout period, vital status will be collected within legal and ethical boundaries (see Protocol Section 10.7.5) for all patients who did not complete the study, and only those with unknown status are considered as lost to follow-up.

4.4. Study Committees

This study includes several independent and expert committees:

- An Executive Committee (EC) oversees the design and conduct of the study and the interpretation of study results.
- An independent Data Monitoring Committee (DMC) reviews accumulating blinded and unblinded safety data from this and other ongoing studies of bempedoic acid approximately 4 times per year to ensure there is no avoidable increased risk of harm to patients. The DMC reviews safety data, reported and adjudicated MACE, and specific clinical laboratory results.
- A blinded independent Clinical Event Committee (CEC) adjudicates designated clinical endpoints, including MACE endpoints, as well as non-CV deaths.
- A blinded independent Diabetes Committee (DC) verifies diagnosis of new-onset type 2 diabetes.
- A blinded independent Tendon Rupture Adjudication Committee (TRAC) adjudicates potential events of tendon rupture.

Each of these committees has its own charter that includes additional details. Adjudicated or verified results for clinical events, diabetes and tendon rupture are maintained in a separate adjudication database.

4.6. Schedule of Events

The schedule of events can be found in Appendix 1.

5. PLANNED ANALYSES

The following analyses will be performed for this study:

- Safety analyses for DMC meetings
- Final Analysis

5.1. Data Monitoring Committee (DMC)

An independent DMC reviews accumulating blinded and unblinded safety in regularly scheduled intervals approximately 4 times per year to ensure there is no avoidable increased risk of harm to patients. DMC reviews safety data, reported and adjudicated MACE, and specific clinical laboratory results. The DMC is responsible for making recommendations about alteration or early termination of the study based upon their review of the blinded and unblinded data.

Analyses for the DMC are provided by an external vendor with a separate unblinded team. There are strict processes in place to ensure blinding for the study team. The details for DMC review procedures are described in the DMC Charter.

5.2. Interim Analyses

[figure not shown]
There are no interim efficacy analyses in this study.

5.3. Final Analyses

This SAP will be finalized prior to the database lock and unblinding of treatment. Additional analyses may be performed as needed but will be clearly marked as ad hoc.

6. ANALYSIS SETS

Inclusion of patients in each analysis set will be finalized prior to the unblinding of the study.

6.2. Full Analysis Set [FAS]

The full analysis set (FAS), used for all the efficacy analyses unless otherwise specified, is defined as all randomized patients, [REDACTED]

[REDACTED] The FAS is also known as the intention-to-treat (ITT) set of patients. Patients in the FAS will be included in their *assigned* treatment group.

Note that patients who participated in the study run-in period only and were not randomized will not be included in FAS.

[figure not shown]
6.3. Safety Analysis Set [SAS]

The safety analysis set (SAS), used for all the safety summaries, is defined as all patients in FAS who received at least 1 dose of double-blind IMP. Patients in the SAS will be grouped according to the *actual* treatment received, in particular:

- patients who were randomized to bempedoic acid but received placebo only will be included in the placebo group;
- patients who were randomized to placebo but received at least one dose of study IMP bempedoic acid will be included in the bempedoic acid group. Note that this does not apply to patients who received commercial bempedoic acid or commercial fixed dose combination of bempedoic acid and ezetimibe.

6.4. Per-Protocol Analysis Set [PPS]

The Per-Protocol Set (PPS) is a subset of FAS that excludes patients with selected major protocol deviations including:

The PPS has the same treatment group assignment as the FAS and is used for sensitivity analyses the primary and key secondary efficacy endpoints. The additional sensitivity analyses of on-treatment and pre-cross-in LMT analyses will also be conducted using PPS.

7. STUDY DEFINITIONS

7.1. Disposition

Study Completion: the study completion status is recorded on the *Study Completion/Early Termination* CRF. A patient is considered as having completed the study if the patient completed the designated EOS visit during the study closeout period (as determined by the site), or if the patient died during the study (i.e., had not been discontinued prior to death).

Treatment Completion: the treatment completion status is recorded on the *End of Treatment* CRF. A patient is considered as having completed study treatment if the patient is still on-

treatment (i.e., has not permanently discontinued treatment) at the EOS visit during the study closeout period or died within 30 days of last dose. Note that patients who did not complete the study will not be considered as having completed the study treatment.

7.2. Key Study Dates

7.2.1. Definition and Imputation of Key Event Dates

Date of End of Study (EOS): the study completion/early termination date recorded on the “Study Completion/Early Termination” CRF. Note that the patient may have a 30-day post EOS follow-up visit after this.

Date of Study Completion (DSC): For patients who did not complete the study, it is the later of a) the date of EOS and b) the date of the 30-day post EOS follow-up visit. For patients who completed the study, it is the latest date of a) the date of EOS, b) the date of the 30-day post EOS follow-up visit, or c) the date of death. This date is used to calculate the duration of study (follow-up) for each patient and all clinical events that happen during this period are adjudicated.

Date of First Dose of IMP (DFDOSE): for each patient, the DFDOSE is the date/time of administration recorded on the “On-Site Study Medication/ Compliance” CRF at Visit T1. If that field is missing, it is set to be next first date of administration at Visit T3.

Date of Last Dose of IMP (DLDOSE): the date of last dose is recorded on the End of Treatment CRF. In cases of missing either completely or partially, it is imputed as the earliest date of a) the last day of the month (if the month and year are present), or the last day of the year (if only the year is present); b) the Date of EOS; and c) the date of the last IMP dispense plus the number of tablets taken.

Date of Last Visit (DLVISIT): the last date recorded on either the *Visit Date* or the *Telephone Contact* CRFs. For patients who did not complete the study, this must be on or prior to the DSC.

Date of Last Known Alive (DALIVE): for patients whose vital status at the end of study is either alive or unknown, this is the last day when the patient is known to be alive. It is the latest “last known alive date” recorded on the *Survival Status* CRF. If this date is partially or completely missing, it is set to the later of last known alive date with imputation and DSC.

Date of Last Assessment for Non-Fatal Clinical Endpoints (DLASMT): Potential clinical endpoints are assessed every three months either in clinic or by telephone through the Post-EOS Phone visit. For patients who died during the study within 90 days of last visit, the DLASMT is set to the date of death. Otherwise, the DLASMT is set to be DLVISIT. Note that this definition also applies to new-onset diabetes mellitus (NODM) as an efficacy endpoint.

Date of Last Survival Follow-Up (DLSFU): For patients who completed the study, or withdrew consent, or discontinued study and were identified as dead only through survival search (death is not adjudicated), it is the DSC. For all other patients it is the Date of Last Known Alive. This is the last date for survival status follow-up.

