10.7.3. Permanent Discontinuation of Investigational Medicinal Product

There may be situations where it may be necessary for a patient to permanently discontinue IMP.

Investigators should contact the Medical Monitor prior to permanent IMP discontinuation to discuss the situation. **If IMP is permanently discontinued, the patient will remain in the study to be evaluated for concomitant medications, efficacy and safety endpoints until the final study visit.** If the patient is unwilling or unable to return for follow-up visits in person, alternatives such as telephone contact visits per the Schedule of Events, or telephone follow up bi-annually, annually or at the end of the study will be offered. The follow-up frequency will be documented in the eCRF.

The reason for permanent discontinuation of IMP should be documented in the eCRF. If the discontinuation of IMP is due to an AE, the event should be documented in the eCRF. Some possible reasons that must lead to permanent early IMP discontinuation include:

- Female patients who become pregnant or are breastfeeding or who do not agree to use an acceptable method(s) of birth control during the study will be permanently discontinued from IMP
- The patient requests to stop IMP permanently
- The patient study blind is broken
- Patient moves away and it is impossible to come to this or any other trial site for visits as required by protocol.

Some possible reasons that may lead to permanent early IMP discontinuation include:

- In the opinion of the investigator, any AE or a significant change in a laboratory value that warrants permanent discontinuation of IMP therapy. Investigators are advised to call the Medical Monitor prior to making such a decision.
- Illness, condition, or procedural complication (including AEs) affecting the patient's ability to participate or requiring prohibited medication. Investigators are advised to call the Medical Monitor prior to making such a decision.
- Enrollment in any other clinical trial involving an investigational product or enrollment in any other type of medical research judged not to be scientifically or medically compatible with this study. If, after discussion with the study Medical Monitor, it is determined that the patient should not continue IMP, IMP will be discontinued.

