11.3. Assessment of Diabetes

The DC will review and utilize data that is recorded in the eCRF and is available in the clinical laboratory database to verify potential events of new-onset diabetes. The verification will occur beginning from the point where the patient signs the informed consent through 30 days after the patient's last study visit. Verification will be completed according to the guidelines detailed in the DC charter. Sites will continue to follow study procedures for recording diabetes and diabetes-related diagnoses as medical history, AEs, or SAEs.

Criteria for a diagnosis of diabetes for inclusion in the diabetes efficacy and safety populations are described in Section 15.4.

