7.2.5. Time to Event and Date of Censoring

For time-to-event analysis of clinical endpoint events (including new-onset type 2 diabetes), the start date is the date of randomization when the FAS is used, based on the ITT principle. When the PPS is used, the start date is set to be the date of first dose. For composite endpoints, the event date is the date of the first component event.

Patients who did not have any event in question will be considered as censored for the analysis. The date of censoring is determined as the following:

- Fatal events (CV death, fatal MI, fatal stroke, all-cause mortality): censored at Date of Last Survival Follow-Up.
- Non-fatal events and composite endpoints that include both fatal and non-fatal events: censored at the Date of Last Assessment.

Please see Section 18.3 for special censoring rule as applicable to patients from Ukraine as a result of the ongoing conflict.

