7.4.3. NODM as an Efficacy Endpoint

For efficacy evaluation, NODM will be assessed in the subset of patients who did not have diabetes at baseline (No Diabetes), including those patients in the subsets of “prediabetes” and “normoglycemia”, but develop postbaseline new onset type 2 diabetes mellitus, defined by 1 or more of the following criteria according to the 2020 American Diabetes Association (ADA) guidelines (ADA, 2020):

1. Fasting plasma glucose ≥ 126 mg/dL (7.0 mmol/L). Fasting is defined as no caloric intake for at least 8 hours;* or

2. Two-hour post-prandial glucose ≥ 200 mg/dL (11.1 mmol/L) during an oral glucose tolerance test as defined in the ADA guidelines;* or
3. HbA_{1c} measurement $\geq 6.5\%$ (48 mmol/mol);* or
4. In a patient with classic symptoms of hyperglycemia or hyperglycemic crisis, a random plasma glucose ≥ 200 mg/dL (11.1 mmol/L).

*Note: In the absence of unequivocal hyperglycemia, diagnosis requires 2 abnormal test results from the same sample or in 2 separate test results.

The NODM events will be verified by the Diabetes Committee based on the [REDACTED] Diabetes Committee Charter.

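### New-onset diabetes is censored at the last clinic or phone contact, so time after the last glucose or HbA1c sample counts as event-free; an analysis censored at the last sample should be added

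*SAP*

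**What the plan says.** **Censoring date.** For patients who die, SAP 7.2.1 states: "For patients who died during the study within 90 days of last visit, the DLASMT is set to the date of death". For the rest: "Otherwise, the DLASMT is set to be DLVISIT". DLVISIT is "the last date recorded on either the *Visit Date* or the *Telephone Contact* CRFs". The same section then extends the rule: "Note that this definition also applies to new-onset diabetes mellitus (NODM) as an efficacy endpoint". SAP 7.2.5, which names new-onset type 2 diabetes within its scope, applies it: "Non-fatal events and composite endpoints that include both fatal and non-fatal events: censored at the Date of Last Assessment". No laboratory sample is required.

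**Endpoint.** All four criteria in SAP 7.4.3 are glucose or HbA1c results, with the note: "In the absence of unequivocal hyperglycemia, diagnosis requires 2 abnormal test results from the same sample or in 2 separate test results". Protocol 11.3 has the Diabetes Committee work from eCRF entries and from what is "available in the clinical laboratory database to verify potential events of new-onset diabetes".

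**Sampling.** After randomization, HbA1c and fasting chemistry (which includes glucose) are scheduled at Months 3, 6 and 12, every 6 months after that, and at end of study (Protocol 10.6.5 to 10.6.9). Scheduled phone visits and the post-study call draw no blood (Protocol 10.6.7, 10.6.10). For patients who stop study drug and cannot or will not attend, Protocol 10.7.3 says "telephone follow up bi-annually, annually or at the end of the study will be offered".

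**Protocol rule.** Protocol 15.7.1 censors NODM 30 days after last treatment for patients who are lost or stop drug early. Protocol 15.1 lets the SAP prevail where the two differ on analysis.

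**The concern.** A last-contact rule suits MACE, because a patient or relative can report a heart attack or a revascularization by phone. It suits NODM less well. Without a sample, a patient crosses a glucose or HbA1c threshold unseen unless usual care makes the diagnosis and the patient reports it. Under the written rule such a patient stays in the risk set, counted as event-free, until the last call.

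Two results are exposed: the absolute NODM rate in each arm, and the hazard ratio if the amount of unsampled time differs between arms. NODM is a secondary objective and one of the hypotheses stated in Protocol 6.2. The prediabetes subgroup is its main analysis population (SAP 15.3.2).

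**Working it through.** **The plan's own figure.** The documents give no event count, rate or power for NODM. The only sizing figure is 1,620 MACE-4 events. The Schoenfeld formula 4(1.960 + 1.282)²/(ln 0.85)² gives 1,592, and 1,620 events give 90.5% power, so that figure holds. This point does not touch it.

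**Step 1: length of the unsampled gap.** Gap = month of last contact − month of last sample. The figures below add 1 month for the post-study call. Study durations of 24 and about 57.5 months come from Protocol Appendix 1, and 42 months from Protocol 6.3.

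| Last sample | Ends Month 24 | Ends Month 42 | Ends Month 57.5 |
|---|---|---|---|
| Month 3, then phone only | 24 + 1 − 3 = 22 | 40 | 55.5 |
| Month 12, then phone only | 24 + 1 − 12 = 13 | 31 | 46.5 |

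For a patient sampled at end of study the gap is only 20 to 40 days (30 ± 10). For a patient lost after a scheduled phone visit it is about 3 months. Multi-year gaps are therefore permitted, but only for patients who are never sampled again.

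**Step 2: formulas.** Let u be the share of an arm's person-time that is unsampled, and d the share of new cases in that time that are still found and verified.

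- Observed rate ≈ true rate × [1 − u(1 − d)]
- Observed HR ≈ true HR × [1 − u_active(1 − d)] / [1 − u_placebo(1 − d)]

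**Step 3: illustrative size, all inputs assumed.** Suppose 20% to 30% stop drug, 30% to 50% of those become phone-only, and this lasts 1.5 to 2 years of the planned 3.5.

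- Low: u = 0.20 × 0.30 × 1.5/3.5 = 2.6%. High: u = 0.30 × 0.50 × 2/3.5 = 8.6%.
- With d = 0, a true rate of 4.0 per 100 patient-years reads 4.0 × 0.974 = 3.9 to 4.0 × 0.914 = 3.7.
- Equal u in both arms: the HR factor is 1.
- u of 8% active and 5% placebo: 0.92/0.95 = 0.97. Reversed: 0.95/0.92 = 1.03.
- Same imbalance with d = 0.5: 0.96/0.975 = 0.985.

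**Step 4: simulation check of the formulas.** Settings, all assumed: 400,000 patients per arm, placebo rate 4 or 8 per 100 patient-years, follow-up 2 to 4.75 years, and 15% to 30% of patients moving to phone-only contact at a random time. That leaves 7.5% to 15% of person-time unsampled, deliberately a heavier load than in Step 3. The HR columns are for a true HR of 1.00; the two simulated values are for the two rates.

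| u placebo / u active | d | Formula HR | HR, last-contact rule | HR, censored at last sample |
|---|---|---|---|---|
| 15% / 15% | 0 | 1.000 | 1.001, 0.995 | 1.001, 0.995 |
| 12.5% / 15% | 0 | 0.971 | 0.964, 0.967 | 0.993, 0.995 |
| 15% / 12.5% | 0 | 1.029 | 1.038, 1.023 | 1.008, 0.993 |
| 10% / 15% | 0 | 0.944 | 0.949, 0.940 | 1.005, 0.996 |
| 10% / 15% | 0.5 | 0.974 | 0.981, 0.968 | 1.007, 0.996 |

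The last column shows simulation noise of just under 0.01. In the first row a true 4.0 per 100 patient-years reads 3.40 under the last-contact rule and 4.01 when censored at the last sample. With a true HR of 0.85 and 15% unsampled in both arms, the last-contact rule gives 0.856 and 0.855.

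**The case against.** The strongest case on the other side has five parts.

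- **Phone follow-up can find diabetes.** After drug is stopped, phone contacts still collect adverse events and medications (Protocol 10.6). The Diabetes Committee uses eCRF data, and verification runs to 30 days after the last visit (Protocol 11.3). Glucose and HbA1c are not among the analytes masked in Protocol 8.3, so usual care can diagnose and the patient can report. This stands: ascertainment is reduced, not nil.
- **The end-of-study visit includes a sample.** SAP 4.3 requires it in clinic for everyone still in the study. For those sampled there, diabetes is found late rather than missed. But Protocol 10.6.9 allows a remote visit whose minimum data set has no laboratory test, and Protocol 10.7.3 allows phone contact only.
- **An on-treatment NODM analysis exists** (SAP 15.4.2), censored no later than 30 days after the last dose. It removes most off-drug phone time. But it uses the per-protocol set, discards off-drug time that was sampled, and leaves remote visits on drug untouched.
- **Other analyses may exist.** The text of SAP 15.4.4 on additional diabetes analyses is not in the copy reviewed, so a similar analysis there cannot be excluded.
- **Replacing the main rule has a price.** It would drop verified events after the last sample and shorten follow-up of patients who stopped drug, away from the intention-to-treat approach in SAP 7.2.5. This stands.

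A reader might infer three stronger things. First, that the plan counts the time as confirmed diabetes-free: the SAP only keeps these patients at risk until a contact date. Second, that the hazard ratio is biased in favor of bempedoic acid: the documents give neither the amount of unsampled time nor its split by arm, and a reversed split moves the ratio the other way. Third, that the main rule is an error to be replaced: given the detection routes above and the price of replacement, that is debatable.

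**Conclusion.** The point holds in limited form. The written rule counts time after the last glycemic sample as event-free and at risk. For patients followed by phone or remote visits and never sampled again, this can run from about one year to more than four. It lowers the NODM rate in both arms, by about 3% to 9% under the assumptions in Step 3 with no detection by phone, and by half that if half the cases are still found. The hazard ratio is essentially unchanged when arms are balanced. It moves by about 3% for 8% against 5% unsampled time, in a direction set by whichever arm has more.

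These sizes rest entirely on assumed shares of patients stopping drug, moving to phone only and being detected by phone. NODM lies outside the testing hierarchy and its p-value is nominal (SAP 8.3), so the type I error control and the 1,620-event sizing are unaffected. This is a cheap improvement, not a defect that undermines the endpoint.

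**What to change.** 1. In SAP 15.3.2 or 15.4, add a full-analysis-set analysis of time to NODM in the prediabetes and no-diabetes groups. Censor event-free patients at their last fasting-glucose or HbA1c sample, count verified events up to that date, and report it beside the DLASMT analysis. State whether local samples count; SAP 16.3 keeps local results out of the statistical analyses.
2. Tabulate by arm the time from last glycemic sample to DLASMT. This replaces the assumptions above with the trial's own figures.
3. State in the SAP that its NODM censoring rule replaces the rule of 30 days after last treatment in Protocol 15.7.1.

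The cost is one derived date, one added analysis and one extra table, with no new data collection. The downside is that a few verified diagnoses made after the last sample do not count in the added analysis; they remain in the DLASMT analysis.
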